3.2 OVERALL SCHEDULE OF TIMES AND EVENTS

Study Timeline	Baseline ^b (Study Entry)	Week 6 ^c	Week 12 ^c	Follow-up Visits (every 12 weeks) ^c	Study Termination Visit ^k
Informed consent	X				
Inclusion/exclusion criteria	X				
Vital signs ^a	X	X	X	X	X
Physical examination	X				X
6MWT / Borg dyspnea score ^d	X	X	X	X	X
WHO Functional Class	X	X	X	X	X
Clinical laboratory assessments	X		X	X ^e	X
Urine pregnancy test ^f	X	X	X	X	X
Dose titration	X	X	X	X	
NT-proBNP	X			X ^g	
Drug accountability/ Compliance	X	X	X	X	X
AEs	X ^h	X	X	X	X ⁱ
Concomitant medications	X	X	X	X	X
Phone calls ^j	X	X	X	X	X
Pharmacogenomic Sample (Optional)				X ^l	X ^l

Abbreviations: 6MWT, 6-Minute Walk Test; AE, adverse event; NT-proBNP, N-Terminal pro-brain natriuretic peptide; WHO, World Health Organization

^a Vital signs should be conducted following at least 5 minutes of rest and prior to or at least 30 minutes following the corresponding 6MWT.

^b Baseline/study entry assessments (6MWT/Borg dyspnea score, WHO Functional Class, clinical laboratory parameters, NT-proBNP, vitals, and physical examination) for this study are those collected at the Study Termination Visit from Study TDE-PH-310 and prior to initiation of open-label study drug. Informed consent and inclusion/exclusion criteria are exclusive to this Protocol.

^c Visit windows are ±14 days.

^d 6MWT must be conducted 3 to 6 hours after the last dose of UT-15C. Subject should rest for 5 minutes prior to each 6MWT.

^e During the follow-up visits, clinical laboratory samples should be collected at the first Follow-up Visit and every other Follow-up Visit thereafter.

^f If applicable, for women of child-bearing potential (WOCBP).

^g NT-proBNP should only be collected at the Follow-up Visit # 3 (Week 48).

^h Any AEs that are ongoing at the Study Termination Visit from Study TDE-PH-310 should be recorded as continuing AEs in this open-label study.

ⁱ Any AEs that are ongoing at the Study Termination Visit from Study TDE-PH-311 should be followed for up to 30 days after completion of the Study Termination Visit.

^j Phone calls to the subject should occur at least weekly for the first 12 weeks, and at least monthly thereafter.

^k After the Study Termination Visit is completed, subjects should down titrate the study drug over an appropriate period of time in accordance with their clinical condition. Once the study drug has been discontinued, any remaining supplies should be returned to the clinic for drug accountability.

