3.3.2.2 Physical Examination

A physical examination will be assessed at Baseline as part of Study Termination assessments from Protocol TDE-PH-310 and at the Study Termination Visit.

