7.1.5 Study Termination Visit

When subjects discontinue the study, they will complete a Study Termination Visit. If possible, each subject should remain on study drug until they have completed the Study Termination visit. After the Study Termination Visit is completed, subjects should down titrate the study drug over an appropriate period of time in accordance with their clinical condition. Once the study drug has been discontinued, any remaining study drug should be returned to the clinic for drug accountability. The following assessments will take place at the Study Termination visit:

- Vital signs (following at least 5 minutes of rest)
- Physical examination
- WHO Functional Class
- AE assessment (for AEs ongoing at the Study Termination Visit, assessments to continue for up to 30 days beyond the Study Termination Visit)
- 6MWT/Borg dyspnea score (if possible, the 6MWT is to be initiated 3 to 6 hours after the last dose of UT-15C; Borg dyspnea score to be conducted immediately following 6MWT)
- Urine pregnancy test (for WOCBP)
- Clinical laboratory assessments
- Drug accountability/compliance
- Concomitant medications
- Collection of blood sample for evaluation of pharmacogenomics (optional) *

** If a subject discontinues prior to their next Follow-up Visit, pharmacogenomic samples will be collected at the Study Termination Visit.*

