8 STUDY TERMINATION

8.1 CRITERIA FOR SUBJECT WITHDRAWAL

A subject may voluntarily withdraw or will be withdrawn from the study and/or study drug by the Investigator at any time for reasons including, but not limited to, the following:

- The subject wishes to withdraw from further participation
- A serious or life-threatening AE occurs, or the Investigator considers that it is necessary to discontinue study drug to protect the safety of the subject
- The subject deviated from the protocol
- The subject's behavior is likely to undermine the validity of his/her results
- The subject becomes pregnant

When a subject is discontinued from the study, the Investigator will complete the Study Termination record and provide an explanation, if needed. If UT-15C has been administered, the Investigator should make every effort to perform all Study Termination evaluations following termination of UT-15C treatment but prior to discharge from the study.

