15.3 CLINICAL LABORATORY PARAMETERS

Blood Chemistries	Hematology	Other
Sodium	Red Blood Cell Count	NT-proBNP (plasma)*
Potassium	Hemoglobin	Urine dipstick analysis**
Chloride	Hematocrit	Urine pregnancy test***
Bicarbonate/CO ₂	Platelet Count	
Albumin	White Blood Cell Count (no differential)	
Blood Urea Nitrogen/Urea		
Total Bilirubin		
Indirect Bilirubin		
Direct Bilirubin		
Alkaline Phosphatase		
Alanine Aminotransferase (ALT)		
Aspartate Aminotransferase (AST)		
Gamma-glutamyl transferase (GGT)		
Creatinine		

Visit Test Schedule

Visit	Labs Collected
Baseline/Study Entry****	Chemistries, Hematology, NT-proBNP, urine dipstick, urine pregnancy***
Week 6 Visit	Urine pregnancy***
Week 12 Visit	Chemistries, Hematology, urine pregnancy***
Follow-up Visits*****	Chemistries, Hematology, NT-proBNP*, urine pregnancy***
Study Termination Visit	Chemistries, Hematology, urine dipstick, urine pregnancy***

* NT-proBNP collected at Baseline/Study Entry and Follow-up Visit (Week 48) only

** pH, specific gravity, presence of protein or blood

*** For women of childbearing potential (WOCBP)

**** Baseline/Study Entry clinical laboratory assessments for this study are those collected at the last visit (Study Termination) from study TDE-PH-310 and prior to initiation of open-label UT-15C.

***** During Follow-up Visits, clinical laboratory samples should be collected at the first Follow-up Visit and every other Follow-up Visit thereafter.

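### Protocol 8.1 asks for the Study Termination evaluations after UT-15C has ended, whereas 7.1.5 and schedule footnote k place them before the taper, and the SAP has no on-drug/off-drug rule

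*Protocol*

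**What the plan says.** Protocol 7.1.5, the procedure for the visit, makes on-drug assessment the default: "If possible, each subject should remain on study drug until they have completed the Study Termination visit". The taper comes next: "After the Study Termination Visit is completed, subjects should down titrate the study drug over an appropriate period of time". Footnote k to the schedule in 3.2, attached to the Study Termination column, gives the same sequence: once the visit is done, "subjects should down titrate the study drug over an appropriate period of time in accordance with their clinical condition".

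Protocol 8.1, on withdrawal of subjects, gives the reverse. Where UT-15C has been given, "the Investigator should make every effort to perform all Study Termination evaluations following termination of UT-15C treatment but prior to discharge from the study". Neither section refers to the other.

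On walk timing, schedule footnote d is firm: "6MWT must be conducted 3 to 6 hours after the last dose of UT-15C". Section 7.1.5 relaxes this at the termination visit to where possible.

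The laboratory set in Protocol 15.3 for this visit is "Chemistries, Hematology, urine dipstick, urine pregnancy". The rows for Week 6, Week 12 and the Follow-up Visits contain no dipstick, so this is the only one scheduled after Baseline.

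The SAP uses all available data (sections 7 and 8.2). Section 8.4 bases summaries on nominal visits without windows, although section 8 speaks of visit windows. Sections 11.4 and 11.5 place laboratory and vital-sign results into visits by date. The disposition listing (9.1) carries the date and time of the last dose, and the walk listing (10.1) carries hours since last dose. No planned summary uses either item to separate on-drug from off-drug values.

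**The concern.** Both instructions govern the same evaluations when a subject leaves the study, and they point in opposite directions. A site that acts on 8.1 records exit 6MWD and Borg score, WHO Functional Class, vital signs and laboratory values after the drug has gone. A site that acts on 7.1.5 records them on drug. The visit label is the same in both cases, so the difference can be seen only by comparing dates.

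Long-term safety and exercise capacity are the secondary objectives. An exit value taken off drug does not describe continued therapy. If it sits in a by-visit summary beside on-drug values, the summary describes a mixture whose proportions are not reported. The off-drug values produced by 8.1 are also avoidable, because many of these subjects could have been assessed before the taper.

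**Working it through.** The plan states no figure on this point to reproduce, so the first three steps are textual.

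**1. Order of events**

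| Source | Order |
|---|---|
| Protocol 7.1.5 | evaluations (on drug where possible), taper, stop |
| Protocol 3.2, footnote k | visit, taper, stop |
| Protocol 8.1 | stop, evaluations, discharge |

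**2. Do the two cover different subjects?** Section 7.1.5 covers subjects who discontinue the study. Section 8.1 covers subjects who are discontinued from it, and its only condition is prior receipt of UT-15C, which every treated subject meets. Its reasons include voluntary withdrawal, protocol deviation and pregnancy, in which the subject may still be taking drug when the decision is made. For pregnancy, Protocol 9.4 expects a period of down-titration. The two groups overlap.

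**3. Does the SAP separate the data?** Laboratory tests and vital signs: no; assignment by date allows an off-drug exit value to fall into an ordinary visit. 6MWD, Borg and functional class: not stated; no table in SAP 12.1 is titled for the termination visit, and no text says how its values enter the by-visit tables.

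**4. How far apart are the two timings?** The plan gives no exit taper rate. As an assumption, take the dose-reduction steps in Protocol 6.1 (0.125 or 0.25 mg every 12 to 24 hours) and two illustrative doses. Days = (dose / step) × interval.
- 2.5 mg TID: from 2.5/0.25 = 10 steps × 12 h = 5 days, to 2.5/0.125 = 20 steps × 24 h = 20 days.
- 6 mg TID: from 6/0.25 = 24 steps × 12 h = 12 days, to 6/0.125 = 48 steps × 24 h = 48 days.

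**5. What could this do to mean termination 6MWD?** Inputs from Protocol 1.2.4 are the Hodges-Lehmann effects in the two trials on background therapy: +11 m (TDE-PH-301, Week 16, p = 0.072) and +10 m (TDE-PH-308, Week 16, p = 0.089). Assume that stopping loses the whole effect, and treat the estimate as a mean shift. Shift = share walked off drug × effect.
- 25% off drug: 0.25 × 10 = 2.5 m; 0.25 × 11 = 2.75, about 2.8 m.
- 50% off drug: 0.50 × 10 = 5.0 m; 0.50 × 11 = 5.5 m.

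The documents do not give the share, so 25% and 50% are illustrations.

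**The case against.** The best defence is that the sections can be read together. Section 7.1.5 is the dedicated procedure, footnote k agrees with it, and its qualifier already allows for subjects whose drug has stopped. Section 8.1 sits among withdrawal criteria that include stopping drug for safety. A sensible site would assess on drug where it can and otherwise after stopping. This stands in part: many sites would probably act that way, and it is too strong to say that none could reconcile the two. But 8.1 is not written as a fallback, and it asks for every effort towards the off-drug order.

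Several stronger readings are tempting and do not hold:

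- **Breach of the walk window.** A reader might infer from footnote d that an 8.1 walk breaks a mandatory rule. Section 7.1.5 relaxes that rule for this visit.
- **Physical examination.** Protocol 3.3.2.2 schedules it after Baseline only at this visit, so all such results might seem affected. The SAP has no physical-examination endpoint, table or listing, so no summary can mix them.
- **Contaminated 6MWD tables.** The SAP is silent on whether termination walks enter them. That is a gap, not evidence of pooling.
- **A larger 6MWD shift.** The +25.5 m in Protocol 1.2.4 comes from TDE-PH-302, in patients on no approved PAH therapy. SAP 9.3.3 records background therapy at randomization in the parent study, so the background-therapy trials are the closer guide.
- **Low trough as proof of being off drug.** The 0.053 ng/mL pre-morning value in Protocol 1.2.3 is the steady-state trough about 12 hours after the evening dose. In that study, subjects on TID treatment were at about this level each morning.
- **Dose quartiles.** Any distortion of the 6MWD summary by quartile of last dose depends on one reading of a term that the SAP does not define.
- **AE follow-up.** Ongoing AEs "should be followed for up to 30 days after completion of the Study Termination Visit", so the window starts at different points under the two orders. Serious events are followed to resolution, death or loss to follow-up, and survival contact is tied to drug discontinuation, so only ongoing non-serious events are affected.

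**Conclusion.** The contradiction is real and lies in operative text. Followed as written, 8.1 produces off-drug exit data that 7.1.5 is designed to avoid, and the SAP has no rule for handling them. The exposure is clearest for laboratory tests, including the sole scheduled post-baseline dipstick, and for vital signs, where assignment by date could carry off-drug values into by-visit summaries. For walk data the route is unspecified.

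The size is modest. No hypothesis test is planned, so no inferential result is at stake. The 2.5 to 5.5 m illustration rests on complete loss of effect, on BID trial estimates carried over to a TID extension, and on an assumed off-drug share of 25% to 50%. This is worth correcting because it is cheap, not because it threatens the study's conclusions.

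**What to change.** Replace the last sentence of Protocol 8.1 with: *Where possible, Study Termination evaluations should be performed while the subject remains on UT-15C and before down-titration (Section 7.1.5); if UT-15C has already been stopped, they should be performed as soon as possible and before discharge from the study.*

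In SAP 8.4, flag any Study Termination assessment made after the last UT-15C dose date as off drug. Keep flagged values out of the on-treatment by-visit summaries in 10.1 to 10.3, 11.4 and 11.5, and report them separately.

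The cost is one protocol sentence, which can go into the next amendment since Protocol 13.1 requires approval of any change, and a little programming. No new visit or data item is needed, because the last dose date is already in the SAP 9.1 listing. The limitation is that subjects assessed in mid-taper are counted as on drug. A finer split by pre-taper dose may not be possible, since SAP 9.3.5 has dosing collected monthly and a short taper can fall between records.

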8 STUDY TERMINATION

8.1 CRITERIA FOR SUBJECT WITHDRAWAL

A subject may voluntarily withdraw or will be withdrawn from the study and/or study drug by the Investigator at any time for reasons including, but not limited to, the following:

- The subject wishes to withdraw from further participation
- A serious or life-threatening AE occurs, or the Investigator considers that it is necessary to discontinue study drug to protect the safety of the subject
- The subject deviated from the protocol
- The subject's behavior is likely to undermine the validity of his/her results
- The subject becomes pregnant

When a subject is discontinued from the study, the Investigator will complete the Study Termination record and provide an explanation, if needed. If UT-15C has been administered, the Investigator should make every effort to perform all Study Termination evaluations following termination of UT-15C treatment but prior to discharge from the study.

8.2 CRITERIA FOR TERMINATING THE STUDY

The study may be stopped at any time if, in the opinion of the Investigator and/or Sponsor, continuation of the study represents a serious medical risk to the subjects. This may include,

but is not limited to, the presence of serious, life-threatening, or fatal AEs, or AEs that are unacceptable in nature, severity, or frequency. The Sponsor reserves the right to discontinue the study for any reason at any time.

8.3 CRITERIA FOR DISCONTINUING THE SITE

The study may also be terminated at a given center if:

- The Principal Investigator elects to discontinue the study
- The Sponsor elects to discontinue the study at the site
- International Council for Harmonisation (ICH) Good Clinical Practice (GCP) or applicable regulations are not observed
- The protocol is repeatedly violated or critical violations are documented
- Changes in personnel or facilities adversely affect performance of the study

9 ADVERSE EVENT REPORTING

9.1 DEFINITIONS

9.1.1 *Adverse Event*

An AE is any untoward medical experience occurring to a subject during a clinical study whether or not it is related to the study drug. An AE may include an intercurrent illness, injury, or any other concomitant impairment of the subject's health, as well as abnormal laboratory findings if deemed to have clinical significance. AEs may also include worsening of an existing symptom or condition or pre/post-treatment events that occur as a result of protocol-mandated procedures.

9.1.2 *Serious Adverse Event*

An SAE is an AE occurring at any dose that results in any of the following outcomes:

- Death
- A life-threatening AE
- Inpatient hospitalization or prolongation of existing hospitalization
- A persistent or significant disability/incapacity
- A congenital anomaly/birth defect

In addition, important medical events that may not result in death, be life threatening, or require hospitalization may be considered serious when, based upon appropriate medical

judgment, they may jeopardize the subject and require medical/surgical intervention to prevent one of the outcomes listed above. Examples of such medical events include allergic bronchospasm requiring intensive treatment in an emergency room or at home, blood dyscrasias or convulsions that do not result in hospitalization, or the development of drug dependency or drug abuse.

Life threatening means that the subject was, in the view of the Investigator, at immediate risk of death from the event as it occurred. It does not mean that the event, had it occurred in a more severe form, might have caused death.

9.1.3 Adverse events associated with progression of PAH

Expected AEs that may be related to the progression of a subject's PAH are defined in Appendix 15.5. All events that occur during the course of the study that are included on this list and felt to be related to the progression of the disease by the Investigator should not be recorded as AEs in the eCRF as these PAH symptoms will be evaluated and recorded as an efficacy endpoint and/or will be captured as disease-related events.

However, each event must be recorded as an AE/SAE in the eCRF, if it meets 1 or more of the following criteria:

- There is a reasonable possibility that it may have been caused by study drug.
- It is serious.
- It has occurred at greater than expected severity (intensity, frequency, or duration).

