1.2.3 Clinical Pharmacology

In solution, both treprostinil sodium and treprostinil diethanolamine are disassociated from their respective salt counter-ions and exist as the freely ionized form of treprostinil. As a result, the bioactive form present in the bloodstream is identical irrespective of the selection of the counter-ion. Given this premise, the development of this new diethanolamine salt of treprostinil is expected to retain the bioactivity and safety profile of treprostinil sodium.

The most frequent adverse events (AEs) associated with Remodulin in clinical trials of patients with PAH were related to the pharmacological properties of Remodulin and were generally not serious. These prostacyclin-related AEs included diarrhea, headache, and nausea. Remodulin has not been associated with any significant changes in laboratory parameters or end-organ toxicity. The safety profile noted in the open-label extension study, with much longer durations of exposure and a larger, more diverse patient population, was consistent with the profile noted in the controlled trials. To date, over 17,000 subjects and patients have been exposed to Remodulin. This number includes patients who have received single administration, to patients receiving continuous infusion for greater than 10 years.

UT-15C has been administered to approximately 1800 subjects in Phase 1–3 clinical trials. UT-15C doses of up to 3 mg BID have been administered to healthy volunteers and patients with PAH have received up to 27.5 mg 3 times daily dosing (TID) in the ongoing Phase 1–3 development program. The average exposure is approximately 2 years; the longest exposure is almost 7 years.

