- PROBABLE - there is a reasonable causal relationship between the study drug and the SAE. The event responds to dechallenge. Rechallenge is not required

ACTION TAKEN

- TEST AGENT DOSE MODIFICATION*
- Dose Increased - the dose or regimen of the test agent was increased
- Dose Not Changed - the dose or regimen of the test agent was not changed
- Dose Reduced - the dose or regimen of the test agent was decreased
- Drug Interrupted - administration of the test agent was stopped temporarily
- Drug Withdrawn - administration of the test agent was stopped permanently and not restarted
- Unknown - changes to the administration of the test agent cannot be determined

*NOTE: Only the last test agent action should be recorded in the eCRF.

OUTCOME

- Fatal – The study subject died
- Not Recovered / Not Resolved – The AE was ongoing
- Recovered / Resolved – The AE resolved
- Recovered / Resolved with Sequelae – The AE is considered resolved however there is a residual sequelae
- Recovering / Resolving – The AE is improving but is not yet completely recovered / resolved
- Unknown – The outcome of the AE cannot be determined

15.5 EXPECTED EVENTS ATTRIBUTABLE TO THE PROGRESSION OF PULMONARY ARTERIAL HYPERTENSION (SYSTEM ORGAN CLASS AND PREFERRED TERM, VER. 16.0)

Abdominal pain (Gastrointestinal disorders; ABDOMINAL PAIN)	Hemoptysis (Respiratory, thoracic & mediastinal disorders; HAEMOPTYSIS)
Anorexia (Metabolism and nutrition disorders; ANOREXIA)	Hypoxia (Respiratory, thoracic & mediastinal disorders; HYPOXIA)
Ascites (Gastrointestinal disorders; ASCITES)	Loss of consciousness (Nervous system disorders; LOSS OF CONSCIOUSNESS)
Cardiac arrhythmia (Cardiac disorders; ARRHYTHMIA)	Nausea (Gastrointestinal disorders; NAUSEA)
Cardiac arrest (Cardiac disorders; CARDIAC ARREST)	Edema (General disorders and administration site conditions; OEDEMA)
Heart failure (including exacerbation of) (Cardiac disorders; CARDIAC FAILURE)	Orthopnea (Cardiac disorders; ORTHOPNOEA)
Chest pain (General disorders and administration site conditions; CHEST PAIN)	Pallor (Vascular disorders; PALLOR)
Cardiovascular collapse (Vascular disorders; CIRCULATORY COLLAPSE)	Palpitations (Cardiac disorders; PALPITATIONS)
Cor pulmonale (Cardiac disorders; COR PULMONALE)	Cool extremities (General disorders and administration site conditions; PERIPHERAL COLDNESS)

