Cough (Respiratory, thoracic & mediastinal disorders; COUGH)	Pulmonary arterial hypertension, exacerbation of (Vascular disorders; PULMONARY ARTERIAL HYPERTENSION)
Cyanosis (Cardiac disorders; CYANOSIS)	Sudden death (Cardiac disorders; SUDDEN DEATH)
Dizziness (Cardiac disorders; DIZZINESS)	Syncope (Cardiac disorders; SYNCOPE)
Dyspnea at rest (Respiratory, thoracic & mediastinal disorders; DYSPNOEA)	Vasovagal reaction (Nervous system disorders; SYNCOPE VASOVAGAL)
Dyspnea on exertion (Respiratory, thoracic & mediastinal disorders; DYSPNOEA EXERTIONAL)	Tachycardia (Cardiac disorders; TACHYCARDIA)
Paroxysmal nocturnal dyspnea (Cardiac disorders; DYSPNOEA PAROXYSMAL NOCTURNAL)	Vomiting (Gastrointestinal disorders; VOMITING)
Exercise intolerance (General disorders and administration site conditions; EXERCISE TOLERANCE DECREASED)	Weight loss (Investigations; WEIGHT DECREASED)
Fatigue (General disorders and administration site conditions; FATIGUE)	Weight gain (Investigations; WEIGHT INCREASED)

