11.2 DISEASE-RELATED EVENTS

Disease-related events will be listed by the subject number, treatment group in parent study, and events (yes/no). The summary will include the number (percent) of subjects who reported each symptom by treatment group in the parent study and overall. Disease-related events include abdominal pain, anorexia, ascites, chest pain, cool extremities, cor pulmonale, cough, cyanosis, dizziness, dyspnea, general edema, hemoptysis, fatigue, hypoxia, loss of consciousness, nausea, orthopnea, pallor, palpitations/cardiac arrhythmia, paroxysmal nocturnal dyspnea, pulmonary hypertension exacerbation, syncope, tachycardia, weight loss/gain, vasovagal reaction, and vomiting.

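### Nausea may be recorded as an AE or as a PAH event depending on the investigator's attribution, and no planned table counts subjects across both, so its incidence could be understated

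*Protocol*

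**What the plan says.** Protocol 9.1.3 sets the recording rule. A listed event that the investigator feels is due to PAH progression "should not be recorded as AEs in the eCRF as these PAH symptoms will be evaluated and recorded as an efficacy endpoint", and the sentence goes on to allow capture as a disease-related event as an alternative or in addition. The section then adds an override: "each event must be recorded as an AE/SAE in the eCRF, if it meets 1 or more of the following criteria". The first criterion is "There is a reasonable possibility that it may have been caused by study drug"; the others are seriousness and greater than expected severity. Protocol 3.3.2.4 repeats the drug-causation criterion.

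The Appendix 15.5 list includes "Nausea (Gastrointestinal disorders; NAUSEA)" and "Vomiting (Gastrointestinal disorders; VOMITING)". Protocol 1.2.3 says of the parenteral form: "These prostacyclin-related AEs included diarrhea, headache, and nausea". Protocol 1.2.4 counts nausea among the effects expected with prostanoids in TDE-PH-302.

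SAP 11.2 handles the diverted events: "Disease-related events will be listed by the subject number, treatment group in parent study, and events (yes/no)". They are summarised as the number and percent of subjects per symptom, by parent-study arm and overall, in Table 14.3.1.8. AEs go to Tables 14.3.1.1 to 14.3.1.7 and 14.3.1.9. SAP 12.1 lists no table that joins the two.

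**The concern.** Protocol 9.1.1 defines an AE without regard to relatedness, so a reader will take Table 14.3.1.2 as all-cause incidence. For symptoms on the Appendix 15.5 list it is not: entry depends on what the investigator thinks caused the event. Nausea is the clear case because the protocol treats it both as an expected PAH symptom and as an effect of the drug class.

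The study is open-label and has no control group, so no comparator can show whether nausea was attributed correctly. Long-term safety is a secondary objective, and the incidence of a named drug effect is one of the figures readers will take from this study.

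**Working it through.** The plan states no incidence or attribution figure, so there is nothing to reproduce. The check traces where a nausea event can go and then asks what the planned outputs can recover.

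**1. Routes for one nausea event (Protocol 9.1.3, SAP 11.1, 11.2 and 12.1)**

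| Event | AE page required? | Planned tables |
|---|---|---|
| Not attributed to PAH progression | Yes | AE tables |
| Attributed to PAH, but a drug cause is reasonably possible | Yes | AE tables |
| Attributed to PAH, and serious or worse than expected | Yes | AE tables |
| Attributed to PAH, non-serious, expected severity, no reasonable possibility of drug cause | No | 14.3.1.8 only |

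**2. All-cause incidence.** The last row is absent from Tables 14.3.1.2 and 14.3.1.9 even if every attribution is correct. A subject whose only nausea falls in that row does not count as having nausea in the AE tables. This follows from the rule itself.

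**3. Drug-caused incidence.** Let p be the true proportion of subjects with drug-caused nausea. Let m be the share of those subjects whose events were all attributed to PAH and met no override criterion. Then

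incidence shown in the AE table = p × (1 − m).

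Neither p nor m is in the documents; both are assumed here. With p = 30% and the enrolment ceiling of 850 (Protocol 3.5):

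| m | AE table shows | Subjects missing |
|---|---|---|
| 0 | 30.0% | 0 |
| 10% | 30% × 0.90 = 27.0% | 850 × 0.30 × 0.10 = 25.5, about 26 |
| 25% | 30% × 0.75 = 22.5% | 850 × 0.30 × 0.25 = 63.75, about 64 |
| 50% | 30% × 0.50 = 15.0% | 850 × 0.30 × 0.50 = 127.5, about 128 |

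For p from 20% to 40%, the shortfall p × m is 2 to 4 percentage points at m = 10% and 10 to 20 points at m = 50%. It is zero at any p when m = 0.

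**4. Can the reader recover the combined figure?** Let A be the percentage with nausea in the AE table and D the percentage in Table 14.3.1.8. A subject may be in either or both. The percentage with nausea from any source therefore lies between max(A, D) and A + D (capped at 100%). Unless the cap applies, that interval is as wide as the smaller of A and D. A subject-level count is needed to close it.

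**5. How many terms are affected?** The protocol names five drug effects in humans in 1.2.3 and 1.2.4: diarrhea, headache, nausea, flushing and jaw pain. Only nausea is in Appendix 15.5. The appendix has 34 terms. SAP 11.2 covers 29 of them in 26 groups, because it merges the two dyspnea terms, palpitations with arrhythmia, and weight loss with weight gain (29 − 3 = 26). Five have no counterpart in SAP 11.2: cardiac arrest, heart failure, cardiovascular collapse, sudden death and exercise intolerance. A non-serious, PAH-attributed case of one of these could appear in neither set of tables.

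**The case against.** The strongest reply is the override. A reasonable possibility of drug cause is a low threshold, and the protocol itself names nausea as a drug effect, so a careful investigator should send most doubtful nausea to the AE page. Applied as written, the rule loses no drug-caused event. That stands, and it makes understatement of drug-caused nausea a risk, not a demonstrated bias. It does not settle the matter. Under Appendix 15.4 an event with a reasonable causal link to concurrent disease can be classed as not related, so nausea judged due to PAH can fail the override on the protocol's own definitions. Nor does the override restore the all-cause count.

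A second reply is that nothing is lost: Table 14.3.1.8 reports the symptom, and subject-level Listings 16.2.6.4 and 16.2.7 exist. This is also right. The gap is in the planned summaries, not in data collection.

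Several stronger readings are tempting but not supported:

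- *The diverted symptoms are promised as an efficacy endpoint that the SAP lacks.* The sentence in 9.1.3 is satisfied by capture as disease-related events, which SAP 11.2 provides.
- *The disease-related records are undated.* SAP section 8 puts the assessment date and study day in listings; only an onset date is not named.
- *Table 14.3.1.8 omits every serious case.* The documents do not say that an event on the AE page is removed from the disease-related record, and the eCRF is not available.
- *Vomiting, anorexia and weight loss are equally documented drug effects.* Protocol 1.2.2 reports vomitus in dogs, and lower food consumption and weight gain in rats and dogs. These documents do not name the three terms as effects in humans.

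**Conclusion.** The point holds as a reporting gap. Tables 14.3.1.2 and 14.3.1.9 exclude any nausea diverted under 9.1.3, and no planned output shows how many subjects had nausea from either source. Whether drug-caused nausea is also understated depends on attribution that this uncontrolled study cannot check.

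A reader might infer that the incidence of the drug's side effects is understated as a matter of fact. The documents do not support that: the shortfall in drug-caused incidence is zero if the override works perfectly, and no attribution share is given from which to estimate it. The 27% to 15% range rests wholly on an assumed 30% incidence and assumed misattribution of 10% to 50%. The conclusion applies clearly to nausea; diarrhea, headache, flushing and jaw pain are not on the list and are unaffected.

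**What to change.** Add one supportive table to the SAP, by parent-study arm and overall. It should give the number and percent of subjects with each SAP 11.2 symptom recorded as an AE/SAE or as a disease-related event, with each subject counted once. Use the SAP 11.2 groupings, since pooled terms cannot be separated as specified. Present the result as an upper bound on drug-caused incidence that does not depend on attribution. Restrict it to subject counts, because the yes/no records may not support an event rate per patient-year.

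Footnote Tables 14.3.1.2 and 14.3.1.9 to say that events attributed to PAH progression under Protocol 9.1.3 are excluded unless they met an override criterion. State in SAP 11.2 how the five unmatched Appendix 15.5 terms are reported.

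I would not remove terms from Appendix 15.5. The SAP preface already cites protocol amendment 6, and changing the collection rule now would make earlier and later nausea records incomparable.

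The cost is one table and two footnotes, using data already collected. The nausea percentages may look less favourable and will include nausea truly due to PAH, so the table needs that caveat.
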